3.9.2 Prognostic Factor Analysis

Prognostic factors or predictors of treatment efficacy for the primary outcome (HRSD) and major secondary outcome measures (MADRS, BSS, BDI, and VR-36) at each time point of the baseline, end of acute treatment, and end of follow-up, will be explored using demographic information and baseline assessments such as age, baseline severity, type of comorbidity (PTSD, substance abuse, or both), duration of illness, prior treatment resistance, concomitant medication use, and possibly their interaction with the treatment. The analyses will be performed on all ITT, completer, and fully compliant populations. Linear or generalized linear mixed regressions will be used to model moderate effect with the factors described above on the treatment efficacy, depending on whether the outcome measure is continuous or categorical. The modeling approach is the same as described in the corresponding sections of the primary and secondary outcome analyses (Tables 3.9.5a-c).

In the event that a multiple regression does not converge when all covariates are included, the model will be refit by dropping the problematic covariate from the model and perhaps investigating it in a separate single-covariate model.

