3.7.1 Primary Efficacy Analysis

3.7.1.1 Primary Endpoint Analysis

The primary endpoint is the proportion of subjects in each treatment group who achieve “remission” from depression at the end of the acute treatment phase (after a maximum of 30 sessions). “remission” is assessed by a HRSD score ≤ 10 at the end of the acute treatment session (after a maximum of 30 sessions). For patients who dropout before completing the acute treatment phase will be considered treatment failures for the primary analysis on remission rates. The primary null hypothesis is that there is no difference between the treatment and sham groups in the proportion of subjects who are remitted during the acute treatment phase. The primary variable is defined in Section 2.4.1.

Logistic regression will be used for the primary endpoint ($Y = 1$ if remitted,

otherwise $Y = 0$) analysis on the ITT population with treatment group as the testing factor (x). The following covariates will be included in the model: PTSD diagnosis (yes/no as assessed by SCID, z_1), History of substance abuse (yes/no as assessed by SCID, z_2), and Site (9 participating sites, z_3). Given the remission probability $p = \Pr(Y = 1 | x, z_1, z_2, z_3)$ the basic model is defined as follows:

$$\log it(p) = \ln\left(\frac{p}{1-p}\right) = \beta_0 + \beta_1 x + \beta_2 z_1 + \beta_3 z_2 + \beta_4 z_3$$

In the event that the logistic regression does not converge when all covariates are included, the model will be refit by dropping the covariates from the model one at a time in the following order until convergence is obtained.

- a. History of substance abuse
- b. PTSD diagnosis
- c. Site

The number and percentage of subjects in remission at the end of the acute treatment will be summarized and compared using Pearson χ^2 test (Table 3.7.1a). Odds ratio and 95% confidence interval (CI) will be presented using SAS PROC GENMOD. If the coefficient for treatment effect is significant (i.e., the confidence interval for the odds ratio does not include 1), then the null hypothesis will be rejected (McCullagh and Nelder, 1989). The significant level for each covariate coefficient in the model will best determined by Wald test (Table 3.7.1b).

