3.7.1.2.3. Remission Rates from Baseline to the Acute Treatment (Short term efficacy)

These endpoints are the proportions of subjects in each treatment group who are remitted at end of acute treatment. The null hypothesis is that there is no difference between the rTMS and sham groups in the proportions of subjects who are remitted across those time points after the acute treatment. The criteria to define the

remission are described in Section 3.7.1. The number and percentage of subjects' remission at the baseline and end of each five sessions the acute treatment will be summarized (Table 3.7.5). Odds ratio and 95% confidence interval (CI) will be presented using SAS PROC GENMOD. SAS PROC GENMOD will be used to run logistic regressions and odds ratios and their 95% confidence intervals will be presented. Further, the generalized linear mixed model will be applied to test the differences of the proportions of subjects' remission across all the time point (Breslow and Clayton 1993). The link function will be logit. SAS PROC GLIMMIX will be used to analyze the data (Tables 3.7.5a-c). The generalized linear mixed model will include three covariates, PTSD diagnosis, History of substance abuse, and Site.

3.7.1.2.4. Remission Rates from End of the Acute Treatment to End of the Follow-up (Long term efficacy)

These endpoints are the proportions of subjects in each treatment group and the data collected from the end of acute treatment to the end of follow-up. The analytic technique is parallel to those described above in Section 3.7.1.2.3. The null hypothesis is that there is no difference between the rTMS and sham groups in the proportions of subjects who are remitted across those time points from the end of the acute treatment to the end of follow-up. The results will be shown in Tables 3.7.6a-c).

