3.7.1.2.5. HRSD Score Over Time

HRSD score at the baseline, end of each treatment block, and end of every four week follow-up time will be tested between the two treatment groups using SAS PROC GLM at each visit. A mixed regression model will be used to test the main effects of treatment using SAS PROC MIXED across all time visits. The model will include week, treatment and treatment by week interaction adjusted for the baseline. A means model will be assumed. An unstructured covariance model will be used in the analysis. If the model fails to converge a compound symmetry covariance matrix will be assumed. The restricted maximum likelihood (REML) method will be used to estimate the covariance parameters. If the treatment by week interaction is not statistically significant then this term will be removed from the final model. The repeated factor will be visit; all other variables will be considered as fixed effects. The model is defined as follows:

$$Y_{ijk} = \mu + \tau_k + B_j + \varepsilon_{ijk}$$

where Y_{ijk} is the HRSD scores measured on k^{th} treatment and on j^{th} visit for i^{th} subject, μ is the overall mean, τ_k is the mean effect of the treatment and the interaction, B_j is the random effect, and ε_{ijk} is the error (Laird et al 1982). The sample sizes, least-squares means, and standard deviations will be presented at each visit by treatment arm for each study visit (Tables 3.7.7a-c). The assumptions relating to the mixed-effects model will be reviewed by examining residual graphs. Scatter plots of residuals will be used to examine deviations from normality and to assess lack-of-fit. The least square means (LS-means) and their standard errors at each visit will be plotted by treatment groups (Figures 3.7.3a-c).

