3.7.2.1.1. MADRS Score Overtime

MADRS score at the baseline, end of each treatment block, and end of every four week follow-up time will be tested between the two treatment groups using SAS PROC GLM at each visit (Tables 3.7.9a-c). A mixed regression model will be used to test the main effects of treatment using SAS PROC MIXED. The model will include visit, treatment and treatment by visit interaction adjusted for the baseline. A means model will be assumed. An unstructured covariance model will be used in the analysis. If the model fails to converge a compound symmetry covariance matrix will be

assumed. The restricted maximum likelihood (REML) method will be used to estimate the covariance parameters. If the treatment by visit interaction is not statistically significant then this term will be removed from the final model. The model is described in Section 3.7.1.2.5. The sample sizes, least-squares means, and standard deviations will be presented at each visit by treatment arm for each study visit (Tables 3.7.9a-c). The assumptions relating to the mixed-effects model will be reviewed by examining residual graphs. Scatter plots of residuals will be used to examine deviations from normality and to assess lack-of-fit. The least square means (LS-means) and their standard errors at each visit will be plotted by treatment groups (Figures 3.7.4a-c).

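### In the prognostic analysis of remission, the non-convergence rule can remove factors according to the outcome data, and the comorbidity factor may duplicate covariates already in the model

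*SAP*

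**What the plan says.** SAP section 3.9.2 explores predictors of HRSD, MADRS, BSS, BDI and VR-36 outcomes. The candidates include age, baseline severity, duration of illness, prior treatment resistance, concomitant medication and "type of comorbidity (PTSD, substance abuse, or both". Interactions with treatment are included only as a possibility. The models are not written out: "The modeling approach is the same as described in the corresponding sections of the primary and secondary outcome analyses".

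The remission models already hold the two conditions. Section 3.7.1.1 lists "PTSD diagnosis (yes/no as assessed by SCID, z_1), History of substance abuse (yes/no as assessed by SCID, z_2" together with site. For repeated remission, section 3.7.1.2.3 states "The generalized linear mixed model will include three covariates, PTSD diagnosis, History of substance abuse, and Site". The score models do not hold them. For HRSD score (section 3.7.1.2.5), "The model will include week, treatment and treatment by week interaction adjusted for the baseline". For MADRS (section 3.7.2.1.1), "The model will include visit, treatment and treatment by visit interaction adjusted for the baseline", and the BDI, BSS and VR-36 sections use the same wording.

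On non-convergence, section 3.9.2 provides for "dropping the problematic covariate from the model and perhaps investigating it in a separate single-covariate model". It neither defines a problematic covariate nor gives an order. Section 3.7 refers efficacy models to the fixed dropping order of section 3.7.1, but section 3.1.2 lets a specific section override a general policy, so the rule in 3.9.2 governs here.

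**The concern.** Two features of section 3.9.2 bear on the remission outcome.

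**Dropping rule.** In a logistic model with few events, non-convergence often means separation: some level of a factor, or some factor-by-arm cell, has no remitters. A rule that then removes the factor selects on the outcome. The table of predictors would be silent on such a factor, and a reader could not tell a factor that was dropped for lack of remitters from one that was uninformative.

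**Comorbidity factor.** Type of comorbidity is a function of PTSD (yes/no) and substance abuse (yes/no). If those two covariates stay in the model, most or all of the new factor is redundant. Redundancy does not stop a fit from converging, so the non-convergence rule would not catch it. A p-value could be printed that answers a different question from the one its label suggests.

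**Working it through.** **Inputs from the SAP.** Section 2.6: 180 per arm, remission 6% on sham and 16% on rTMS, stated power 81%. Section 3.1.2: two-sided 0.05. Section 3.7.1.1: PTSD, substance abuse and nine sites as covariates. The SAP gives no figure for the prognostic analysis, so factor prevalences and effects below are assumptions.

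**The plan's own figure.** Two-proportion test with continuity correction:
- numerator: 0.10 − 1/180 − 1.96 × √(2 × 0.11 × 0.89/180) = 0.0298
- denominator: √((0.06 × 0.94 + 0.16 × 0.84)/180) = 0.0326
- power: Φ(0.0298/0.0326) = Φ(0.915) = 82.0%, against 81% stated (86.1% uncorrected, 83.3% by Fisher's exact test). The planning rates are usable.

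**Expected remitters.** 180 × 0.06 + 180 × 0.16 = 10.8 + 28.8 = 39.6.

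**Chance that a whole level has no remitters.** Take a factor held by 10% of patients, so 18 per arm. Hold the arm rates at 6% and 16% and solve 0.9 p₀ + 0.1 p₁ = arm rate, with p₁ set by the odds ratio. The chance is (1 − p₁,sham)^18 × (1 − p₁,rTMS)^18.

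| Odds ratio, holder v non-holder | p₁ sham | p₁ rTMS | Chance of no remitting holder |
|---|---|---|---|
| 1 | 0.0600 | 0.1600 | 0.328 × 0.043 = 1.4% |
| 0.3 | 0.0202 | 0.0584 | 0.692 × 0.339 = 23% |
| 0.1 | 0.0070 | 0.0208 | 0.881 × 0.685 = 60% |

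**Sparse null levels are exposed too.** At the average rate of 11%, a level of 10 patients has no remitter with probability 0.89^10 = 31%, and a level of 20 with probability 0.89^20 = 9.7%.

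**Factor-by-arm cells.** With four equal comorbidity classes (assumed), each sham cell has 45 patients. One cell is empty of remitters with probability 0.94^45 = 6.2%, and at least one of four with probability 1 − (1 − 0.062)^4, about 23%.

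**The single-covariate refit.** If the whole level has no remitters, the level is still empty in a model with that factor alone, so its log odds ratio has no finite estimate there either. If only a factor-by-arm cell is empty, a model pooled over arms can succeed: for an unrelated 10% factor, no sham holder remits with probability 0.94^18 = 33%, but no holder in either arm with probability 1.4%.

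**Rank of the comorbidity factor.** The base model has intercept, treatment, PTSD, substance abuse and eight site terms: rank 12.
- Four classes, including neither: rank 13. The factor adds 1 degree of freedom, the PTSD-by-substance-abuse product, where a stand-alone factor would have 3.
- The three listed classes only (patients with at least one condition): rank stays 12. The factor adds 0.
- Base model without the two conditions, as in the score models: the factor adds its full 3.
- Treatment-by-comorbidity: adds 3 with four classes and 2 with three, so it stays estimable.

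A trial fit with the redundant columns converged, with the same deviance as the model holding the product term (274.278).

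**What the 1-degree-of-freedom test sees.** Simulation with 180 per arm, 6% v 16%, nine sites, substance abuse 50%, PTSD odds ratio 0.4 and no interaction (prevalences and effect assumed):

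| PTSD prevalence | Comorbidity test beside the two covariates rejects | Joint PTSD + substance-abuse test rejects |
|---|---|---|
| 50% | 5.7% | 65% |
| 30% | 7.6% | 51% |

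With no effect at all, the comorbidity test rejected 6.9% of the time. It is essentially blind to a main effect of either condition.

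**The case against.** The strongest reply is that section 3.9.2 carries over a modelling approach, not an explicit covariate list. On an ordinary reading, the comorbidity factor could be the way the two conditions enter the prognostic model, replacing the yes/no terms. The section also names no source for the factor. Section 3.7.1.1 uses SCID, while section 2.5.2.5 also defines PTSD by CAPS score, and the overlap is exact only with the SCID variables. This stands, and it makes the second point conditional.

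A reader might go further and infer that comorbidity has no valid test at all. The SAP does not support that. The HRSD-score, MADRS, BDI, BSS and VR-36 models contain neither condition, so nothing is lost there. The treatment-by-comorbidity test, which serves the moderator purpose stated in section 2.5.2, remains estimable. Section 3.7.1.1 already gives Wald tests for the PTSD and substance-abuse coefficients in the primary remission model.

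A reader might also infer that the strongest predictors are the likeliest to vanish. That is too strong. Sparse levels of unrelated factors can be dropped as well, continuous factors have no level to be empty, linear models do not separate, and the optional single-covariate model can rescue a factor when only one arm's cell is empty. Simulated separation in 33% to 54% of trials with no true effect requires all the optional treatment interactions (26 parameters) and an assumed 80% to 90% on concomitant medication. Without interactions it is 7% to 10%.

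Finally, the analysis is exploratory.

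**Conclusion.** Both points hold for the remission outcome in section 3.9.2, within limits.

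**Dropping rule.** It lets the outcome data decide which categorical factors stay. The chance that a 10% factor has no remitting holder rises from 1.4% when it is unrelated to 23% at an odds ratio of 0.3 and 60% at 0.1. These figures rest on the planning rates and on an assumed prevalence and effects. They give the chance of an empty level, not of every cause of non-convergence.

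**Comorbidity factor.** If the two covariates are retained and the same SCID variables are used, its main-effect test in the remission models has 1 degree of freedom with a neither class and 0 without, so it is not the intended test.

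The primary analysis is unaffected. Correction is worthwhile because it is cheap and because section 2.5.2 gives moderator analysis as the reason for collecting these measures.

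**What to change.** In SAP section 3.9.2:

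1. **Replace the dropping rule.** For remission at a single time point, keep all prespecified factors and refit with Firth penalised likelihood (PROC LOGISTIC, FIRTH option, profile-likelihood intervals). For the repeated remission model in PROC GLIMMIX, where that option does not apply, report the Firth fit at the single time point instead of deleting the factor.
2. **Recode comorbidity in the remission models.** Use PTSD, substance abuse and their product, with treatment interactions, in place of a separate type factor, so that patients with neither condition form the reference class. State that the SCID variables of section 3.7.1.1 are the source.

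The cost is SAP wording and one SAS option, with no new data. The downside is slight shrinkage of the Firth estimates towards the null. The score models can stay as written.

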3.9.3 Additional Baseline Analyses

3.9.3.1 Trauma History Questionnaire (THQ)

THQ is a 24 item self-report measure that examines experiences with potential traumatic events including crime, general disaster, and sexual and physical assault, using a yes/no format. The summary statistics of THQ scores for each event and overall score will be tabulated. Student t test using SAS PROC TTEST or Wilcoxon test using SAS PROC NPAR1WAY will be performed to test score differences between the two treatment groups (Table 3.9.6).

3.9.3.2. Blessed Orientation Memory Concentration Test (BOMC)

The BOMC assesses level of cognitive impairment using 3 orientation questions, counting backwards from 20 to 1, months backwards, and the name and address memory phase. The testing result is measured by a weighted error score with

a maximum 28. The summary statistics of BOMC scores for each event and overall score will be tabulated. Student t test using SAS PROC TTEST or Wilcoxon test using SAS PROC NPAR1WAY will be performed to test score differences between the two treatment groups (Table 3.9.7).

3.9.3.3. Life Stressor Checklist-Revised (LSC-R)

The LSC-R is a self-report assessment for traumatic or stressful life events. The questionnaire includes 30 life events of natural disasters, physical or sexual assault, death of a relative and other events using a yes/no format. In addition, a five point intensity scale for each event is used to weight on the event score. The summary statistics of LSC-R score (0-30) and its weighted score (0-150) will be tabulated. Student t test using SAS PROC TTEST or Wilcoxon test using SAS PROC NPAR1WAY will be performed to test score differences between the two treatment groups (Table 3.9.8).

3.9.3.4. Lifetime Drinking History (LDH)

As described in Section 2.5.2.1, the LDH is a structured interview designed to provide quantitative data on patterns of alcohol consumption. This assessment is performed only at baseline. The summary statistics of the total alcohol consumption, typical and maximum alcohol consumption per occasion, average daily and average monthly intake both for the last six months (current drinking) and for lifetime (lifetime drinking history) will be tabulated. Student t test using SAS PROC TTEST or Wilcoxon test using SAS PROC NPAR1WAY will be performed to test score differences between the two treatment groups (Table 3.9.9).

3.9.3.5. Antidepressant Treatment History Form (ATHF)

The ATHF provides detailed information about antidepressant resistance for a patient to be qualified for the study. The form collects drug name, dosage, blood level, duration, number of weeks in treatment, reason stopped, outcome, overall confidence rating, resistance rating, and adequate trials. The drug resistance criteria are based on adequate trial score. if the score is >2 , the patient meets the drug resistant criteria. The summary statistics of the adequate trial score will be tabulated (Table 3.9.10). Student t test using SAS PROC TTEST or Wilcoxon test using SAS PROC NPAR1WAY will be

performed to test score differences between the two treatment groups, and Pearson χ^2 test using SAS PROC FREQ will be used to test the patient drug resistant eligibility between the two treatment groups.

3.9.3.6. Structured Clinical Interview for DSM-IV (SCID)

The semi-structured interview is to make the major DSM-IV diagnosis criteria for subject eligibility. There are four diagnostic modules (mood disorders, psychotic symptoms, substance use disorder, and anxiety disorders) with two aspects, i.e. lifetime prevalence (absent, subthreshold, threshold), and symptomatic diagnosis criteria in past month (absent, present). The summary statistics of each category of lifetime prevalence and symptomatic diagnosis criteria in past month will be tabulated (Table 3.9.11a-b) for each diagnostic module. Pearson χ^2 test using SAS PROC FREQ will be used to test the differences between the two treatment groups.

3.9.3.7. Laboratory Data

Hematology, chemistry, liver function, and endocrinology are analyzed at the study site local laboratories during screening process. For hematology, complete blood counts (CBC) including red blood cells (RBC), white blood cells (WBC) and platelets, quantitative analyses for hemoglobin, hematocrit, and other measurement are performed. For blood chemistry, serum is separated according to standard procedures, and quantitative analysis is performed for the following analytes: sodium, potassium, chloride, carbon dioxide, glucose, creatinine, and blood urine nitrogen (BUN) and urea. For liver function, albumin, total bilirubin, direct bilirubin, alanine aminotransferase (ALT/SGPT), aspartate aminotransferase (AST/SGOT), alkaline phosphatase (ALP), and total protein are measured. For endocrinology, TSH, total T3 and T4 are measured. All these laboratory measurements are captured as normal, abnormal not clinically significant, abnormal clinically significant, and not done. The data are tabulated by treatment groups based on the above categories.

(Table 3.9.12).

3.9.4 Control Questionnaire Analysis

As described in 2.5.5, the questionnaire is designed to check the possibility that the blindness is bleached during the treatment. The survey is done before first

treatment session, after first treatment session, and end of the study by the local site investigator, the TMS treater, the study coordinator, and the participant. The distribution of the best guess of the treatment assignment and the confidence level of the guess will be tabulated in Table 3.9.13a-b by the treatment groups and tested by Pearson χ^2 test using SAS PROC FREQ. For those with moderate or higher confidence level, the concordance of the true and the guessed treatment assignment will be performed using κ statistic as shown in Table 3.9.14.

5.0 APPENDICES

Appendix 5.1 Study Schema

Appendix 5.2 Schedule of Assessments

Assessment		2-4 weeks Screening/ Baseline	Acute Treatment Phase						Follow-up Phase							
			4 - 11 weeks						24 weeks (6 months)							
			End of Session Number ¹						PRN Taper weeks			Weeks				
			5	10	15	20	[25]	[30/ last	1	2	3	4	8	12	16	20
86	Consent	S*														
01	Screening Form	S														
02	Randomization Form	B*														
03	Baseline	S														
04	Medical History	S														
05	Physical Exam	S							x							
06	Labs	S														
07	Structured Clinical Interview for DSM-IV-TR (SCID-I)	S														
08	Current/Past ATHF	S														
09	Lifetime Drinking History	B														
10	Clinician Administered PTSD Scale (CAPS)	B							x							x
11	Trauma History Questionnaire (THQ)	B														
12	Life Stressor Checklist-revised (LSC-R)	B														
13	Six-Item Blessed Orientation-Memory-Concentration (BOMC)	S														
14	Pregnancy Test	S ²	Every 4 weeks													
15	Medication Use	S	x	x	x	x	x	x	x	x	x	x	x	x	x	x
16	Study Visit Form		x	x	x	x	x	x	x	x	x	x	x	x	x	x
17	Audiometry	S						x								x
18	rTMS Treatment Log		x	x	x	x	x	x								
19	rTMS Taper Log								x	x	x					
20	Hamilton Rating Scale for Depression (HRSD) and MADRS	S ²	x	x	x	x	x	x				x	x	x	x	x
21	Beck Depression Inventory (BDI)	B	x	x	x	x	x	x				x	x	x	x	x
22	Quick Inventory of Depressive Symptomatology (QIDS-C16)	B	x	x	x	x	x	x				x	x	x	x	x
23	Columbia-Suicide Severity Rating Scale (C-SSRS)	S														
24	Columbia-Suicide Severity Rating Scale (C-SSRS) F/U		x	x	x	x	x	x	x	x	x	x	x	x	x	x
25	Beck Scale for Suicidal Ideation (BSS)	S	x	x	x	x	x	x	x	x	x	x	x	x	x	x

Assessment		2-4 weeks Screening/ Baseline	Acute Treatment Phase						Follow-up Phase							
			4 - 11 weeks						24 weeks (6 months)							
			End of Session Number ¹						PRN Taper weeks			Weeks				
			5	10	15	20	[25]	[30/ last	1	2	3	4	8	12	16	20
26	Beck Hopelessness Scale	S	x	x	x	x	x	x	x	x	x	x	x	x	x	x
27	Quality of Life (VR 36)	B					x									x
28	Neuropsychological Battery	B					x									x
29	DAST	S					x									x
30	PTSD Checklist (PCL)	B					x									x
31	MAST	S					x									x
32	STAXI-2	S	x	x	x	x	x	x	x	x	x	x	x	x	x	x
TLFB	Alcohol/Drug Timeline Followback (TLFB)		x	x	x	x	x	x	x	x	x	x	x	x	x	x
33	Urine Tox Screen/Alcohol Test	S		x		x		X		x		x		x		x
34	Termination Form ³															x
35	Control Questionnaire	Before and after the 1 st treatment														x
36	Protocol Deviation	As required														
37	Adverse Events (AE) and ADE and Serious Adverse Events (SAEs) and UADE	As required														

*B= Baseline

*S= Screening

¹ Sessions 21-25 (block 5) and 26-30 (block 6) may not be required if patient goes into remission earlier

² Must be conducted within 7 days prior to randomization

³ Termination Form will be completed at the end of the study OR when a patient decides to end study participation prior to the study completion date; i.e., a patient decides to withdraw or leave the study for any reason, withdraws consent, or is suspended from the study.

